8.10. Suicidality

Any suicide attempt in the past, suicidal ideation with a specific plan in the past 2 years prior to screening (visit 1), or current suicidal ideation will result in patient exclusion.

Investigators will inquire about and evaluate suicidal ideation, plan, and behavior based on their clinical judgement and refer patients to psychiatric care as appropriate.

Any suicide information collected will be listed.

9. TOLERABILITY VARIABLES AND ANALYSIS

Spontaneous reports of injection site reactions will be recorded as adverse events according to the following severity assessment criteria:

- Spontaneous reports of injection site erythema, induration, and ecchymosis will be recorded according to measurements: 5 to ≤50 mm (mild), >50 to ≤100 mm (moderate), and >100 mm (severe).
- Spontaneous report of local pain after the injection will be recorded as mild, moderate, or severe according to patient's self-report.
- Appropriate treatment may be provided if necessary, in which case it must be recorded as concomitant medication.

Tolerability will be assessed by the following:

• the number (%) of patients who fail to complete the study due to adverse events

Spontaneously reported local tolerability findings will be listed and summarized descriptively.

10. PHARMACOKINETIC ANALYSIS

Pharmacokinetic plasma concentration results (fremanezumab) are collected at visit 2, visit 3, visit 4, and visit 8 and patients must return to the study center after visit 2, visit 3, or visit 4 for 2 additional blood sampling visits (see study protocol for details). Samples from patients who received the active IMP will be analyzed for the concentration of fremanezumab using a validated method. Samples from patients who were randomized to receive placebo will not be analyzed.

The plasma concentration results will be tabulated descriptively at each planned sampling time point by treatment group. Concentration values that are below the lower limit of quantitation (<LLOQ) will be treated as 0, and missing values will be ignored in the concentration summary tables. Individual pharmacokinetic concentration data will be summarized and listed in the CSR.

The pharmacokinetic data from this study will be pooled with the data from other fremanezumab studies and assessed for comparability. Summary statistics of fremanezumab pharmacokinetic parameters model-based predictions of weight-adjusted exposures will be compared and will be reported separately.

11. IMMUNOGENICITY ANALYSIS

Samples from patients who receive the active IMP will be analyzed for ADA using a validated method. Samples from patients who receive placebo will not be analyzed.

Blood samples (10 mL for the predose sample at visit 2; 6 mL for all other samples) will be collected prior to dosing at visit 2, visit 4, visit 8 (EOT), and visit 9 (EOS) for immunogenicity testing.

Summary of immunogenicity results will be provided, and the incidence of immunogenicity will be calculated. This analysis will be reported separately.

12. PLANNED INTERIM ANALYSES

Two interim analyses are planned. The first interim analysis is planned when the last patient has completed the double-blind period and will use the double-blind period data. A second interim analysis is planned following the end of the open-label period and will use the open-label period data.

The inferential analysis of efficacy variables for comparison between each fremanezumab treatment group (monthly dose and quarterly dose) and placebo will be done at the time of the first interim lock. The appropriate method for type 1 error control will be applied to the first interim analysis.

Efficacy analysis for the open-label portion of this study is considered exploratory and mainly descriptive. This analysis will be done at the time of the second database lock.

13. STATISTICAL SOFTWARE

All data listings, summaries, and statistical analyses will be generated using SAS[®] version 9.4 or later.

14. CHANGES TO ANALYSES SPECIFIED IN THE STUDY PROTOCOL

The following endpoint has been removed in the SAP due to the necessary data not being collected:

• mean change from baseline in the monthly average number of days with most bothersome symptoms during the 12-week period after the 1st dose of IMP

The wording of the following endpoint has been changed as shown.

Wording from protocol:

• mean change from baseline (day 0) of patient satisfaction, as measured by the PGIC scale, at 4 weeks after the last (6th) dose of study drug

New wording in SAP:

• assessment of patient satisfaction, as measured by the Patient Global Impression of Change (PGIC) scale, at visit 8

A multiple imputation analysis has been added in Section 6.2.3.2 as an additional sensitivity analysis of the primary estimand to assess the sensitivity of the primary analysis to missing data assuming the data is missing not at random.

The definitions for CM and EM have been modified; CM is defined as having ≥ 15 headache days during the baseline period whilst < 15 headache days during the baseline period is classed as EM.

The following analysis has been removed in the SAP due to minimal COVID-19 diagnoses occurring:

• Missing data or visits due to the COVID-19 pandemic will be evaluated for the primary and secondary endpoints. COVID-19 may have an impact on patients' migraine symptoms, with headache reported to be a common complication as a result of contracting the disease. All COVID-19 cases will be included in the primary analysis; however, observations following COVID-19 diagnosis will be discarded from the calculation of the monthly average endpoint. The data handling strategy will be detailed in the statistical analysis plan.

The following subgroup analysis has been removed in the SAP due to disease severity being collected daily rather than just once during the baseline period:

• Patients by disease severity (Mild, Moderate, Severe)

APPENDIX A. ELECTRONIC HEADACHE DIARY QUESTIONNAIRE

	The following questions are referring to yesterday (00:00 - 23:59)
A1	Did you have a headache yesterday?
A2	Did you have at least two (2) consecutive hours of headache yesterday?
A3	What was the greatest severity that your headache reached yesterday at any time?
A4	How many total hours did you have a headache of any severity yesterday?
A5	How many total hours of moderate or severe headache did you have yesterday?

	The following questions are referring to yesterday (00:00 - 23:59)
B1	Was your headache pain worse on one side (left or right) of your head yesterday?
B2	Was your head pain throbbing, pounding or beating like a drum yesterday?
В3	Did you have a stomach ache, feel sick to your stomach or did you throw up yesterday?
B4	Did light bother you more than when you didn't have a headache (did you experience photophobia)?
B 5	Did sounds bother you more than when you didn't have a headache (did you experience phonophobia)?
B6	Did you have trouble seeing normally or did you see spots, stars, wavy lines, or flashes during your headache yesterday? (This is different from "light bothers you")
B7	Did you have feelings such as numbness or tingling in any part of your body or face around the time of your headache?
B 8	Before your headache started, did you notice any of the usual signs that a headache is coming yesterday? This could include seeing spots, stars, wavy lines, or flashes or having trouble speaking, feeling dizzy or having tingling, numbness or weakness in your arms or legs.

	The following questions are referring to yesterday (00:00 - 23:59)
C1	Did you take any prescription medications yesterday for your headache/migraine?
C2	Which of these medications did you take yesterday?
C3	Did you use any non-prescription medication in an effort to get relief from your headache/migraine yesterday?

	The following questions are referring to yesterday (00:00 - 23:59)
E1	Did you have problems falling asleep yesterday?
E2	Which of the following situations best describe your work/school performance yesterday, when you did not have a headache?
E3	What would better describe how you felt in general yesterday?
E4	How much of the time yesterday did you find it difficult to concentrate on what you needed to do?
E5	On average, how much of the time yesterday were you very tired, asleep, or feeling drained?
E6	Which of the following situations best describe your ability to perform household chores yesterday, when you did not have a headache?
E7	How engaged were you with your partner's or children's activities yesterday, when you didn't have a headache?
E8	Overall, how interested were you in doing daily activities yesterday?

APPENDIX B. LOGICS FOR ENDPOINTS DERIVATION

			Migraine day Pr	: 1 of th imary	e following 5 op endpoint	tions		
		OPTION 1			OPTION 2			
Part 1	1	A1	YES	1	A1	YES		
	2	A2	YES	2	C1	YES		
			AND	3	C2	ERGOT OR TRIPTAN		
		ONE OF T	THE FOLLOWING		OPTION 3			
Part 2	1	A3	Moderate/Severe					
	2	B1	YES	1	A1	YES		
	3	B2	YES	2	C2	Medication Provided		
	AND							
				3	C3	YES		
		ONE OF T	HE FOLLOWING		OPTION 4			
Part 3	1	B3	YES					
				1	A1	YES		
	2	B4	YES		AND			
		AND			ONI	E OF THE FOLLOWING		
		B5	YES	2	B6	YES		
					OR			
	OPTION 5: PROBABLE MIGRAINE				B7	YES		

	OPTION	5: PROBABI	LE MIGRAINE		
If Part 1 and Part 2 met from option 1, Part 3 needs ONLY					
one of the following:					
Part 3	B4		YES		

Part 3	B4	YES
	B5	YES

If Part 1 and Part 3 met from option 1, Part 2 needs ONLY one of the following:

Part 2	1	A3	Moderate/Severe
	2	B1	YES
	3	B2	YES
If Dent 0 and Dent 0 meet from anti- 1 Dent 4 meeted ONI			

If Part 2 and Part 3 met from option 1, Part 1 needs ONLY the following:

Part 1	1	A1	YES

Headache day of at least moderate severity: 1 of the following 3 options					
OPTION 1					
1	A1	YES			
2	A2	YES			
3	A3	Moderate or Severe			
OPTION 2					
1	A1	YES			
2	C1	YES			
3	C2	ERGOT OR TRIPTAN			
OPTION 3					
1	A1	YES			
2	C2	Medication Provided			
3	C3	YES			

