6. EFFICACY ANALYSIS

6.1. General

For the purposes of this study;

- CM is defined as headache occurring on ≥ 15 days during the screening period.
- EM is defined as headache occurring on <15 days during the screening period.

All e-diary data collected during the screening period, regardless of the duration beyond 28 days (e.g., 30 days), will be included and analyzed. There will be no exclusion of any e-diary data during the screening period.

A migraine day is endorsed when at least one of the following situations occurs:

- A calendar day (0:00 to 23:59) demonstrating at least 2 consecutive hours of a headache meeting the criteria for migraine with or without aura
- A calendar day (0:00 to 23:59) demonstrating at least 2 consecutive hours of a headache meeting the criteria for probable migraine, a migraine subtype where only 1 migraine criterion is missing
- A calendar day (0:00 to 23:59) demonstrating a headache of any duration that was treated with migraine-specific medications (triptans and ergot compounds)

A headache day of at least moderate severity is endorsed when at least 1 of the following situations occurs:

- a calendar day (0:00 to 23:59) demonstrating at least 2 consecutive hours of headache of at least moderate severity
- a calendar day (0:00 to 23:59) demonstrating a headache of any duration that was treated with migraine-specific acute medications (triptans and ergot compounds)

The derivation logic for both migraine day and headache day of at least moderate severity is presented in Appendix B.

In addition, a headache day of any severity is endorsed when at least 1 of the following situations occurs:

- a calendar day (00:00 to 23:59) demonstrating at least 2 consecutive hours of headache of any severity
- a calendar day (0:00 to 23:59) demonstrating a headache of any duration that was treated with migraine-specific acute medications (triptans and ergot compounds)

The endpoint of headache hours of at least moderate severity is obtained directly from the corresponding electronic headache diary device question (Question A5).

The endpoint of days of use of any acute headache medication is obtained directly from the corresponding electronic headache diary device questions (Question C1=Yes or C3=Yes and C2 has a medication present).

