6.2.4. Supplementary Estimands

A supplementary estimand will estimate treatment effect in the hypothetical scenario where no one early terminates from study drug. The estimand is the difference in adjusted means between fremanezumab group and placebo group in the population that comprises the patients in the double-blind mITT analysis set for the change from baseline in the monthly average number of migraine days during the 12-week period after the 1st dose of IMP where the ICEs are handled as per Table 2.

Intercurrent event	Strategy
Patient early terminates from the IMP	Hypothetical: For patients in the monthly dosing regimen group who early terminate from study drugs, observations collected more than 4 weeks after the last dose will be treated as missing. In formula (1) an average is taken so these values which are left missing due to early termination will be replaced with the average for that month of those in the same treatment group who do not early terminate. Missing observations prior to early termination will not be replaced.
Patient receives the wrong IMP due to medication errors	Treatment policy ¹

Table 2: Intercurrent Event Strategies: 1st Supplementary Estimand

Intercurrent event	Strategy
Patient receives a rescue medication due to	Treatment policy ¹
worsening symptoms	

¹Treatment policy: if observations are collected after the occurrences of the ICEs, the observations will be included in the calculation of the primary endpoint for the primary analysis.

A second supplementary estimand will estimate treatment effect in the hypothetical scenario where no one takes rescue medication (rescue medication is indicated by a response of Yes to C1 or C3, and a medication present in response to C2 of the electronic headache diary device). A rescue medication for migraine is defined as medication that does not abort a migraine, but masks the pain for a few hours until the migraine runs its course.

The estimand is the difference in adjusted means between fremanezumab group and placebo group in the population that comprises the patients in the double-blind mITT analysis set for the change from baseline in the monthly average number of migraine days during the 12-week period after the 1st dose of IMP where the ICEs are handled as per Table 3.

Table 3: Intercurrent Event Strategies: 2 nd Suppl	lementary Estimand
---	--------------------

Intercurrent event	Strategy
Patient early terminates from the IMP	Treatment policy ¹

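### SAP Appendix B Option 3 counts any headache with a C2 medication entry and C3=Yes as a migraine day and as a moderate-severity day, while SAP 6.1 limits the medication-only route to triptans and ergots

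*SAP*

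**What the plan says.** SAP 6.1 gives written definitions of both day types. For the migraine day, the medication-only route is a day "demonstrating a headache of any duration that was treated with migraine-specific medications (triptans and ergot compounds"). Protocol 9.5 has the same item, and inclusion criterion g in protocol 4.1 also names only triptans and ergot derivatives. For the headache day of at least moderate severity (below, a moderate-severity day), SAP 6.1 again accepts only triptans or ergots as the medication-only route. The other route is a day "demonstrating at least 2 consecutive hours of headache of at least moderate severity". Even a headache day of any severity needs a day "demonstrating at least 2 consecutive hours of headache of any severity", or a triptan or ergot.

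SAP 6.1 then hands over to the appendix: "The derivation logic for both migraine day and headache day of at least moderate severity is presented in Appendix B".

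In Appendix B, Option 2 requires A1=Yes, C1=Yes and a C2 entry that is an ergot or triptan. Option 3 requires A1=Yes, C2 "Medication Provided" and C3=Yes. The second table, "Headache day of at least moderate severity: 1 of the following 3 options", repeats Option 3. In Appendix A, A1 asks whether there was a headache, C1 asks about prescription medication, C2 asks which medication was taken, and C3 asks about non-prescription medication.

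SAP Section 14 lists changes from the protocol, including the new chronic and episodic migraine definitions. It does not list a change to either day type. The SAP Introduction says that the SAP takes precedence over the protocol and that differences will be explained in the study report.

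**The concern.** The SAP defines the same variable in two ways. A programmer working from 6.1 and one working from Appendix B would build different primary endpoints from the same diary data.

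The migraine-day rule feeds the primary endpoint, its baseline covariate, the 4-week migraine-day secondary and the 50% responder secondary. The moderate-severity rule feeds a further secondary and that model's own baseline covariate. If the choice is still open when treatment codes are known, it becomes a choice of primary endpoint made with the data in view.

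**Working it through.** The plan gives no figure on this point, so there is none to reproduce. The check compares the rules and then converts days into endpoint units.

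**1. The rules applied to one headache.** Take a mild headache under 2 hours with no migraine features: A1=Yes, A2=No, A3=mild, B items No. Only the medication answers vary. The analgesic row assumes that C2 can be answered when only C3=Yes.

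| C1 | C2 | C3 | SAP 6.1 | Appendix B |
|---|---|---|---|---|
| No | analgesic | Yes | neither day type | both (Option 3) |
| Yes | NSAID | Yes | neither day type | both (Option 3) |
| Yes | NSAID | No | neither day type | neither |
| Yes | triptan | No | both | both (Option 2) |
| No | triptan | Yes | both | both (Option 3) |

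Rows 1 and 2 are the conflict. Under 6.1 those days are not even headache days of any severity, yet Appendix B scores them as at least moderate. If C2 opens only after C1=Yes, row 1 cannot occur but row 2 still can. Rows 2 and 3 show that Option 3 is not a general any-acute-medication rule either: the same NSAID entry counts or not according to C3. Row 5 shows that Option 3 would still do work if limited to ergots and triptans.

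**2. Is C2 wider than triptans and ergots?** The C2 response list is not shown. Three texts indicate that it is wider: Option 2 has to restrict C2 to ergot or triptan; SAP 6.1 uses C1 or C3=Yes with a C2 entry to mean any acute headache medication; and protocol 6.1.1 includes NSAIDs and acetaminophen among the acute medications recorded in the diary.

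**3. Weight of one day.** Call a day that qualifies under Option 3 but under no rule in 6.1 an Option-3-only day. SAP formulas (1) to (3) give it the weight 28 / (diary days recorded):

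- 12-week average, full diary: 28/84 = 0.33. At 75% compliance (0.75 × 84 = 63 days): 28/63 = 0.44. At the 10-entry minimum in SAP 4.3: 28/10 = 2.8.
- Baseline or 4-week value, full 28 days: 28/28 = 1.0. Baseline with the minimum 21 entries: 28/21 = 1.33.

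**4. Responder status, formula (4).** Assume full diaries and a baseline of 8 days qualifying under 6.1 plus 2 Option-3-only days.

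- On treatment 4 + 2 per month: by 6.1, (8 − 4)/8 = 50%, responder; by Appendix B, (10 − 6)/10 = 40%, non-responder.
- On treatment an Appendix B average of 5, which is 5 × 84/28 = 15 days, of which 1 is Option-3-only. The other 14 give 14 × 28/84 = 4.67. By 6.1, (8 − 4.67)/8 = 41.7%, non-responder; by Appendix B, (10 − 5)/10 = 50%, responder.

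The classification can move in either direction.

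**5. Scale for the treatment difference (a conversion, not a forecast).** Suppose the arms differ on average by k Option-3-only days per patient over 84 days and are balanced at baseline. The difference then shifts by k × 0.333. For k = 0.5, 1 and 2 this is 0.17, 0.33 and 0.67 days. Against the 1.3-day and 1.5-day differences that protocol 1.2.2.2 reports for the episodic-migraine pivotal study, k = 1 is 0.333/1.3 = 26% and 0.333/1.5 = 22%. That benchmark is episodic only, whereas this trial pools both migraine types. The documents give no value for k.

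**The case against.** The strongest defence is that 6.1 expressly delegates the derivation to Appendix B, and Appendix B prints Option 3 for both day types. That could be a deliberate operational rule with the prose abbreviated. The SAP prevails over the protocol, and differences are to be explained in the study report. The rule applies alike to both blinded arms and to baseline, so neither bias nor inflation of the type 1 error has been shown.

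Part of this stands: the documents do not establish which text was intended, and they show no bias. The rest does not remove the conflict. The precedence clause settles protocol against SAP, not one part of the SAP against another, and a study report is written after unblinding. Layout damage is not the explanation either: the migraine-day table is hard to read in the text copy, but the moderate-severity table prints the same Option 3 intact.

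Three stronger readings are tempting and are not supported.

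- A reader might infer that all four secondaries are affected. Days of any acute medication use are taken directly from C1, C2 and C3, so that endpoint has the same values under either rule.
- A reader might cite SAP 6.2.4, where "rescue medication is indicated by a response of Yes to C1 or C3, and a medication present in response to C2" and rescue is "medication that does not abort a migraine, but masks the pain for a few hours", as proof that Option 3 is wrong. Every Option 2 day meets the same coding, so it does not separate the two options.
- A reader might say that the protocol forbids Option 3 for both day types, or that only triptan or ergot days can count. Protocol 9.5 as shown defines only the migraine day, so for the moderate-severity day the conflict lies within the SAP. The drug limit applies only to the medication-only route; headaches meeting the 2-hour criteria also qualify.

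**Conclusion.** The point holds. For both day types, SAP 6.1 and Appendix B give different answers for the same diary entries. The printed algorithm is wider than the stated definition, and no clause in the plan resolves this. The affected quantities are the primary endpoint, its baseline covariate, and the 4-week migraine-day, 50% responder and moderate-severity secondaries.

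The conflict rests on one assumption: that C2 accepts entries other than triptans and ergots on days with C3=Yes, whether or not C1 is also Yes. The texts point that way, but the response list and skip logic are not shown. The per-day weights are exact. The frequency of Option-3-only days, and the size and direction of any effect on the treatment difference, cannot be derived from the documents, so no claim is made that the result would favour either arm. Because the definition of the primary endpoint is at stake, this should be settled before codes are released.

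**What to change.** Before the first interim lock and unblinding, make one rule govern both baseline and post-baseline values.

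- Default: in both Appendix B tables, limit the C2 entry in Option 3 to ergot or triptan. This matches SAP 6.1 and, for the migraine day, protocol 9.5 and inclusion criterion g. Run the wider algorithm as printed as a supplementary derivation.
- If the wider rule is intended: amend the definitions in SAP 6.1, declare the departure from protocol 9.5 for the migraine day in Section 14, and run the current 6.1 definition as a sensitivity analysis.

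The cost is a SAP wording change, a change to the derivation program and one additional analysis. The diary items are already collected, and SAP 2.5.2 already provides for amendments approved before database lock.

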6.1. Assessments of Efficacy

6.1.1. Electronic Headache Diary Device

The primary efficacy endpoint (and secondary and other efficacy endpoints) will be derived from headache variables collected daily using an electronic headache diary device (Table 3). Eligible patients will receive comprehensive training from site personnel on the use of the electronic headache diary device. Site personnel will also instruct patients on the requirement for timely and daily completion of the electronic headache diary. Approximately 75% compliance is needed during the baseline (ie, entry of headache data on a minimum of 21 days) and treatment periods.

On each day, the patient will be asked to record diary data for the previous 24-hour period. Patients may be asked about their performance at work, at school, and when doing household chores (ie, functional assessments). Patients who report headache on the previous day will answer questions about the headache (ie, the number of hours with headache, presence of associated symptoms, and use of acute migraine medications). Additional details regarding the questions patients will answer can be found in the electronic headache diary device training manual.

If a patient fails to complete the diary for the preceding day, the patient will be prompted to enter the missed day's information the next time he/she accesses the electronic headache diary, provided no more than 48 hours has elapsed since completion of that day. If more than 48 hours has elapsed since completion of a diary day, the patient will not be allowed to enter diary information for that day, and it will be considered a missed day.

Rating of headache severity and the duration of headache for each day will be completed in the electronic headache diary. Overall headache duration will be recorded numerically, in hours, as well as number of hours with headache of at least moderate severity.

If headache is reported, then headache severity will be subjectively rated by the patient as follows:

- mild headache
- moderate headache
- severe headache

Patients will also record whether photophobia, phonophobia, nausea, and vomiting are present, and they will record any acute migraine medications (the name of the drug, the number of tablets/capsules, and the dose in milligrams per tablet/capsule) taken on each day. These acute medications are opioids, barbiturates, triptans, ergots, non-steroidal anti-inflammatory drugs (NSAIDs), acetaminophen and their combination products.

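### SAP Appendix B counts moderate-or-worse headache days more loosely than SAP 6.1 defines them, in Option 1 and in Option 3

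*SAP*

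**What the plan says.** SAP 6.1 gives two routes by which a day qualifies. The duration route is "a calendar day (0:00 to 23:59) demonstrating at least 2 consecutive hours of headache of at least moderate severity". The treatment route is "a calendar day (0:00 to 23:59) demonstrating a headache of any duration that was treated with migraine-specific acute medications (triptans and ergot compounds". The section then points the programmer elsewhere: "The derivation logic for both migraine day and headache day of at least moderate severity is presented in Appendix B".

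Appendix B, under "Headache day of at least moderate severity: 1 of the following 3 options", lists:

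- Option 1: A1 = yes, A2 = yes, A3 = moderate or severe.
- Option 2: A1 = yes, C1 = yes, C2 = ergot or triptan.
- Option 3: A1 = yes, C2 = a medication provided, C3 = yes.

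The diary items are in SAP Appendix A. A2 asks "Did you have at least two (2) consecutive hours of headache yesterday". A3 asks "What was the greatest severity that your headache reached yesterday at any time". A5 asks "How many total hours of moderate or severe headache did you have yesterday". C3 asks about non-prescription medication. Protocol 6.1.1 confirms that the diary captures overall headache duration "as well as number of hours with headache of at least moderate severity". SAP 6.1 uses A5 only for the separate headache-hours variable.

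The endpoint is formally tested. SAP Section 7 puts it second of four secondary endpoints. Protocol 9.5.2 lists it last, but the SAP introduction says that the SAP prevails where the two differ.

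**The concern.** In the natural reading of SAP 6.1, the severity condition belongs to the two hours. In Option 1 it does not: A2 carries duration without severity, A3 carries severity without duration, and nothing links them. The derived variable is then peak severity on a day with a two-hour headache of any grade. Option 3 goes further and imposes neither a severity nor a duration condition once a non-prescription drug is recorded, whereas 6.1 reserves the treatment route for triptans and ergots.

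Two programmers, one following 6.1 and the other Appendix B, would count different days from the same diary. The same variable at baseline is also the covariate for this endpoint's model (SAP 6.3.2), so the ambiguity enters both sides of the analysis. If this test fails, the 50% responder and acute-medication endpoints that follow it lose their inferential status.

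**Working it through.** The plan states no figure on this point, so the check sets the two rules against constructed diary days. The inputs are the 6.1 definition, the Appendix B options and the wording of the Appendix A items. The days themselves are invented for illustration.

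| Constructed day | A2 | A3 | A5 (h) | Appendix B now | SAP 6.1 | A5 ≥ 2? |
|---|---|---|---|---|---|---|
| 1. 6 h headache, 0.5 h of it moderate, no drug | yes | moderate | 0.5 | counts (Option 1) | does not count | no |
| 2. 6 h headache, two separate 1 h moderate spells, no drug | yes | moderate | 2 | counts (Option 1) | does not count | yes |
| 3. 6 h headache, 3 moderate hours in a row, no drug | yes | moderate | 3 | counts (Option 1) | counts | yes |
| 4. 1 h mild headache, triptan | no | mild | 0 | counts (Option 2) | counts | no |
| 5. 1 h mild headache, non-prescription drug (not a triptan or ergot) | no | mild | 0 | counts (Option 3) | does not count | no |

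**Option 1.** Day 1 shows the mismatch. Day 3 shows agreement where the moderate hours really are consecutive.

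**Option 2.** Day 4 agrees, so the triptan/ergot route is not in dispute.

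**Option 3.** Day 5 is a second, separate mismatch. A change to Option 1 alone would leave it in place. It would also leave a day like Day 1 counted whenever a non-prescription drug was taken.

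**What A5 can and cannot do.** Two consecutive hours at moderate or worse imply at least two total hours at that severity. With consistent diary answers, requiring A5 ≥ 2 in Option 1 therefore removes only days that cannot meet the 6.1 duration route. The converse fails: Day 2 has A5 = 2 but no two consecutive moderate hours. No diary item records consecutive hours at moderate severity, so 6.1 as worded cannot be derived exactly from this diary.

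**Effect on the treatment difference.** Let e be the number of extra days per 28 days that Appendix B counts beyond 6.1. Before covariate adjustment,

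difference (Appendix B) = difference (6.1) + [(e after − e baseline) on fremanezumab − (e after − e baseline) on placebo].

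The bracket can be positive, negative or zero. It depends on how many qualifying days have A5 below 2, or qualify through Option 3 alone, by arm and period. The documents give none of these counts.

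**The case against.** The best reply is that the 6.1 phrase can be read as a headache rated moderate or worse that lasted two hours. Protocol 6.1.1 has the patient rate headache severity for each day as mild, moderate or severe, and 6.1 hands the derivation to Appendix B. On that reading A2 plus A3 is the definition. It is true that Appendix B is the rule that will be programmed. But the phrase more naturally attaches severity to the hours, the diary collects those hours separately, and this reading does nothing for Option 3.

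It is also fair that the rule is the same in both arms and at baseline, so there is no argument here that type 1 error is inflated. A5 gives only an approximation, and moving to it changes what is counted. Both points stand, which is why rewording 6.1 is an acceptable alternative.

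Three stronger readings are tempting and are not supported:

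- A reader might assume some shift in days and divide it by the 1.8 or 2.1 day differences that Protocol 1.2.2.2 reports for the chronic migraine pivotal study. The shift would be invented. That study enrolled chronic migraine only, and the 2.1 belongs to a regimen with a 675 mg starting dose followed by 225 mg monthly, which is not a regimen in this trial. No percentage should be quoted.
- A reader might infer that a drug which makes long moderate attacks mainly mild gets no credit. Hours at moderate or worse are a separate efficacy variable taken from A5, and the net direction for this endpoint is unknown.
- A reader might take the silence of SAP Section 14 as an undeclared departure from the protocol. That section lists changes from the protocol, and the visible protocol text never defines this day by hours. The inconsistency lies inside the SAP.

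**Conclusion.** The point holds as an internal inconsistency in the SAP for a formally tested secondary endpoint. Appendix B differs from 6.1 in two ways: Option 1 does not tie the two hours to moderate severity, and Option 3 admits any headache treated with a non-prescription drug. The first rests on the natural reading of 6.1 and the second does not. With consistent diary answers, Appendix B should count every day that 6.1 counts and some that it does not. How many more, and whether the treatment difference grows or shrinks as a result, cannot be determined from the documents. It should be settled before unblinding because the endpoint is second in the testing sequence and its definition should not be open once results are known.

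**What to change.** Make one SAP edit before the treatment codes are released for the first interim analysis:

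- In Appendix B, Option 1 for this endpoint, add A5 ≥ 2 hours to the A1, A2 and A3 conditions, for baseline and post-baseline days alike.
- In 6.1, state that A5 records total rather than consecutive hours, so this is the closest rule the diary supports.
- Bring Option 3 and the treatment route in 6.1 into agreement, either by limiting Option 3 to triptans and ergots or by stating in 6.1 that non-prescription treatment also qualifies a day, with the reason.
- Keep the present Appendix B rule as a sensitivity analysis.

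If the sponsor prefers A2 plus A3 as the main rule, for example for comparability with earlier studies, then 6.1 must be restated to describe it, and the A5-based count reported as the sensitivity analysis. Option 3 still has to be reconciled.

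The cost is a short text change and small programming changes. A5 is already collected, so no new data are needed. The downside is small: A5 only approximates consecutive hours, and counts of qualifying days may be lower.
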